18.0 Confidentiality

18.1 Data Security:

Participants are assigned a coded identification number that is used on all data collection measures. This includes a family id (e.g. individual #1 in family #1 is 0001-1). Identifying information necessary for participant contact, such as names,

PROTOCOL TITLE: Comparing Web, Group, and Telehealth Formats of a Military Parenting Program

VERSION DATE: May 4, 2018

addresses, and telephone numbers are kept in locked filing cabinets or in our secure participant database. Access to the online database is restricted to those with valid usernames and passwords and limited to those staff members whose jobs require use of this information for contacting participants. Individuals using this database receive unique and identifiable usernames and passwords. Relational database passwords must be changed on a regular basis. All staff members are required to close password-protected applications or lock their workstations when they are away from their desks. During data analysis all identifying information, with the exception of the participant identification number is removed from the data. No information about identities of the study participants will be published or presented at conferences.

To ensure confidentiality, all information will be coded so that it cannot be associated with any individual. To minimize the risk of loss of confidentiality, the data collected online in this study will be protected by the use of separate databases. The first will include the subject consent forms, first names only and subject ID. Other databases will include the questionnaire data from the project, and participants' study ID will be the only unique piece of information linking the data files to the consent file. Video files of observational assessment tasks will be stored in a separate storage area online. Only study IDs will be used to link videos to questionnaire data. These files will all be password protected and accessible to only a limited number of project personnel. In order to protect participant data during internet based research, the project will use Qualtrics, a sophisticated online data management system that maintains extremely stringent levels of encryption and data storage. Qualtrics is specifically designed to meet and exceed industry standards for Internet security as well as Institutional Review Board (IRB) and Data Safety and Monitoring Board (DSMB) standards for the protection of research participants. For participants, secure servers with registered site certificates provided by VeriSign Internet Trust Services provide for advanced encryption over the wire. To ensure an even greater level of security and confidentiality, Qualtrics also requires that participants are authenticated to gain access to the data entry forms. Participants will receive an email with the survey name specified as a query string parameter in the URL, which is encrypted by SSL. As users move through the data entry forms, the responses are encrypted while in-transit between the browser and Qualtrics's server using SSL (Secure Sockets Layer) and 40, 56, or 128-bit Public Key Encryption. All data collection is performed using the Secure Sockets Layer (SSL) with 128-bit secure key encryption whenever possible. Data will be stored on the Qualtrics server and will be downloaded to U of MN and de-identified data to U of O for analysis.

Qualtrics servers are stored in a locked, well-ventilated room in locked server cabinet/racks and are protected by alarm security. Questionnaires will be designed so that individuals cannot be identified on the basis of their data alone, and as noted above, all identifying information will be stored in a separate database from the data files. All subject identification data will be destroyed at the end of the project. The collected materials will be used only for research purposes; participants' records with identifying information will not be released to anyone without participants' written permission.

PROTOCOL TITLE: Comparing Web, Group, and Telehealth Formats of a Military Parenting Program

VERSION DATE: May 4, 2018

All University of Minnesota, U OF O, ISII and IRIS Media employees who will work on this project, including administrative, research, and production staff, have attended at least one training session on protecting the rights and welfare of human research subjects. The session(s) included an overview of the history of human subjects' protection, an overview of the Belmont Report, a review of IRB policies and procedures, and a discussion of the regulatory requirements regarding informed consent. The University of Minnesota has a mandatory IRB curriculum for all Principal Investigators, which [name] and all other project investigators and staff have completed. IRIS Media has developed a self-directed training program for its employees that includes the videotape entitled "Protecting Human Subjects," and utilizes the web-based training program from the Office of Human Research Protections. In addition, all project staff received adequate training in the responsible conduct of research involving human subjects through participation and completion of the CITI Human Subjects Research Educational Model course (delivered by the NIH).

All data entered into the computerized database will be identifiable by subject code number only. All research staff sign confidentiality agreements. No one except the research staff will have access to records identifying subjects' names at any time. The information gathered will be used only for scientific, educational, or instructional purposes. Finally, the PI will apply for a Certificate of Confidentiality to further protect privacy of each participant and avoid compelled "involuntary disclosure" (e.g., subpoenas) of identifying information about a research subject.

It should be noted that we are not allowed to ask substance use questions to Active Duty participants and will encode the online survey with logic if-then routing that will eliminate those questions from the battery of assessment for active duty participants.

The link between identifiers and code will be maintained for 10 years following the end of data collection.

Data will be kept for ten years following the end of data collection in order to allow sufficient time for analysis of videotaped observations, which are coded using microsocial/second-by-second techniques, and are very time-consuming to code. Following this, videotaped data will be destroyed.

All data will be stored in digital form on secure University of Minnesota servers. Access to files is password protected. Most data will be stored electronically, but some situations may require the use of paper forms

Certificate of Confidentiality has been obtained to provide further protection of our study participants and our data.

Access to data will be restricted to the Project Offices at the University of Minnesota. All space accessible to the public is separated from research offices by locked doors. All staff entrances are secured with locked doors. All paper forms

PROTOCOL TITLE: Comparing Web, Group, and Telehealth Formats of a Military Parenting Program

VERSION DATE: May 4, 2018

will be kept in locked file cabinets. The Department's computing system is protected from outside access. The planned complexity of this system helps increase the security of the local network. Servers maintain logs and generate reports of access attempts, which are reviewed by the Network Administrator. During the analysis of the data, all identifying information with the exception of the subject identification number is removed from the data. No information about the identities of study participants will be published or presented at conferences.

Breaking of confidentiality: There is the risk that we may learn that a child has been abused, neglected, or endangered and need to report it to child protective services. Thus, we will fully inform parents of the limits of confidentiality, both verbally and in writing. Given that the intervention we will be offering teaches non-abusive parenting strategies, we believe that the potential benefits in this area outweigh the risks. Project staff will be properly trained to identify signs of potential child abuse, neglect, or child endangerment, and will report any suspicions immediately to the Principal Investigator. Suspicions of child abuse, neglect, or endangerment will be reported to child protective services in accordance with Minnesota law, and the parents will be told of the report. In addition, those who present an imminent threat of harm to themselves or others will be reported to the proper authorities. Project staff will also be properly trained in responding to parents who are experiencing significant life difficulties and require additional professional assistance. The statement of informed consent will include the following statement: "It is possible that you may experience serious life difficulties that are beyond the ability of the ADAPT program to help you with. This program is not a substitute for professional help for serious difficulties you might be having. If you feel you are having an emergency situation, please seek outside professional help. If you are experiencing serious difficulties, please let us know [project staff email and phone provided] and we will work with you to find resources in your community that can help you." Staff will be equipped with specific guidelines and a referral list for referring parents to specialized treatment for PTSD, substance abuse, depression, domestic violence, other mental illness, and similar problems beyond the scope of ADAPT. Procedures to prevent the violation of confidentiality in accordance with reporting requirements are limited by the mandatory nature of these requirements. Subjects are informed in the consent document that staff must report to authorities 1) physical injury to any child caused by other than accidental means, as required by Minnesota Statutes; and 2) information from a study participant which leads staff to believe a person is in imminent danger of physical harm. Staff will inform parents or guardians if, in the judgment of the professional staff, their child (under 18) is in imminent danger of trying to kill him/herself.

19.0 Provisions to Monitor the Data to Ensure the Safety of Participants – NA

20.0 Provisions to Protect the Privacy Interests of Participants

PROTOCOL TITLE: Comparing Web, Group, and Telehealth Formats of a Military Parenting Program

VERSION DATE: May 4, 2018

20.1 Protecting Privacy:

Assessments are conducted either online or, if in person, in subjects' homes, to ensure convenience for participants. We have conducted in-home assessments in prior studies without problems. Military populations may be especially resistant to coming to a university or hospital setting for assessment or intervention, which is why program activities (for in-person groups) will be held in community locations convenient to participants (i.e. libraries, community centers). As participants are recruited we will determine optimum group locations. For example, given the prevalence of ARNG families in Stillwater, we anticipate that one location will be a library or community center in Stillwater. In each location we will rent a private room with no capacity for those outside to overhear or see what is being said. The University of Minnesota project office in the Department of Family Social Science will be used as a default location for assessments in the event that any family requests not to have a home visit assessment

20.2 Access to Participants: NA

21.0 Compensation for Research-Related Injury

21.1 Compensation for Research-Related Injury: NA

21.2 Contract Language: NA

22.0 Consent Process

22.1 Consent Process (when consent will be obtained):

Initial consent is obtained online. The consent form will be divided to be easily read on separate screens without the need to scroll. Participants will need to check a box indicating that they have read that part of the consent form before they can proceed to the next screen of the consent form. On the last screen, participants will need to check a box saying that they have read the form, asked questions, and understand what they are being asked to participate in before they click the "agree to participate" button. During the online consent, participants will all be offered the opportunity (i) for a phone call to complete the consent process, or (ii) to complete the consent process at the start of the in-home (i.e. in person) baseline assessment. In addition, contact information for researchers (phone and email) is provided on the website and the consent document.

Additionally, assent from minor participants will be obtained at the first in-home visit. Subjects who are randomized to the experimental (intervention) condition will complete an additional consent to participate in the program and for videotaping of the intervention. This additional consent will be gathered during the first group session for those randomized to in-person groups, or online for those randomized to individualized, web-facilitated ADAPT.

22.2 Waiver or Alteration of Consent Process (when consent will not be obtained, required information will not be disclosed, or the research involves deception): NA

22.3 Non-English Speaking Participants: NA

PROTOCOL TITLE: Comparing Web, Group, and Telehealth Formats of a Military Parenting Program

VERSION DATE: May 4, 2018

22.4 Participants Who Are Not Yet Adults (infants, children, teenagers under 18 years of age):

- One parent will give consent for their child, under the age of 18, but who is between 5 and 12 years old per our eligibility criteria, to take part in the study.
- Assent will be obtained by the child assessment technician from the child participant during the first in-home assessment.

22.5 Cognitively Impaired Adults, or adults with fluctuating or diminished capacity to consent: NA

22.6 Adults Unable to Consent: NA

23.0 Setting

23.1 International Research: NA

23.2 Community Based Participatory Research: NA

23.3 Research Sites:

- Research will be conducted at the following locations: participants' homes, neutral community location, University of Minnesota (ADAPT offices), and at the Michigan ADAPT office.
- Recruitment will take place in the following ways: Recruitment flyers promoting the study will be distributed to our partners (NG, VA, M-SPAN). In addition, the PI has been invited by the MN ARNG to present at reintegration workshops which are mandatory for all soldiers returning from OEF/OIF deployment, and flyers will be handed out there. Flyers provide the phone and email contact information for the researchers, and the study site URL. The website guides parents to a brief explanation of the project, and a description of project confidentiality and its limits. Refer a friend post cards will be distributed to previous ADAPT study participants and current participants (as recruitment occurs). A recruitment/outreach booth will be set-up at the MN State Fair on Military Appreciation Day.

Interested participants will be directed to an anonymous online screening instrument. This screen determines eligibility based on the above stated inclusion and exclusion criteria. Eligible participants will next complete a brief contact information form, followed by an online informed consent that will provide information about study risks, benefits and about the possibility of being randomly assigned to either an intervention (E) group or SAU comparison group. In reintegrating families with two at-

PROTOCOL TITLE: Comparing Web, Group, and Telehealth Formats of a Military Parenting Program

VERSION DATE: May 4, 2018

home participating parents/caregivers, each will complete a separate informed consent.

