1.0 Objectives

1.1 Purpose:

The overarching goal of this study is to advance research on family-based prevention of negative child outcomes for reintegrating Operation Enduring Freedom/Operation Iraqi Freedom personnel by evaluating different formats of a parenting program, After Deployment, Adaptive Parenting Tools/ADAPT. The ADAPT program is based upon the Parent Management Training-Oregon Model/PMTO, but adapted for military deployed families. We will examine which of three delivery formats of ADAPT is most effective at reducing youth risk behaviors associated with negative childhood outcomes by improving parenting, child, and parent adjustment. There is a clear intent to benefit all subjects in this study (except surveyed teachers), including children.

We will conduct a three-group, two-site randomized trial to test the comparative effectiveness of ADAPT delivery approaches. The study will randomly allocate 360 NGR families to one of three conditions: (i) group-based web-enhanced ADAPT; (ii) individualized web-facilitated ADAPT; or (iii) self-directed web ADAPT.

Thus, specific aims are as follows:

1. Conduct a three-group, two-site randomized trial to test the comparative effectiveness of ADAPT delivery approaches
 - a. Families will complete a pre-intervention baseline assessment and post-intervention follow-up assessments at 6, 12- and 24 months.
2. Test the generalizability of ADAPT effectiveness across three delivery approaches using intent to treat (ITT) analyses
 - a. Test the value-added impact of group-based delivery relative to facilitated and self-directed web approaches
 - b. Comparative effectiveness will be tested by specifying a non-equivalence hypothesis for group based and individualized facilitated relative to self-directed web only

We hypothesize that (1) individualized web-facilitated parenting intervention will be equally effective as the group-based web-enhanced intervention, and (2) both individualized and group-based ADAPT will be more effective than a self-directed web-condition. Effective internet delivery methods will facilitate development of new approaches to engage military families separated by deployment, isolated by geographical location, and in need of strategies to deal with deployment and reintegration stressors, directly addressing limitations and barriers to access to evidence based prevention programs.

PROTOCOL TITLE: Comparing Web, Group, and Telehealth Formats of a Military Parenting Program

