VERSION DATE: May 4, 2018

Analysis of Aim 1: ADAPT comparative effectiveness hypotheses will be tested using standard normal theory Analysis of Variance and multiple regression techniques in structural equation modeling (SEM) with a focus on growth curve analyses for follow up data. We will specify analyses to test Hypothesis 1: NGR families in both the ADAPT group-based condition and the ADAPT web-facilitated condition will show greater pre-post improvements in observed parenting, and parent, child, and couple functioning relative to the self-directed web condition; and Hypothesis 2: ADAPT group-based condition will be equally effective as the individualized ADAPT web-facilitated condition.

Analyses for Hypothesis 1 of Aim 1. We will employ standard normal theory pre-post Analysis of Variance and structural equation modeling (SEM) growth curve analyses for the long-term follow up. For the immediate pre-post analyses we will conduct a 3 group by 2 repeated measures Analysis of Variance for parenting, child, and couple functioning constructs focusing on the comparison of change across the Group Based, Individualized Facilitated, and Self-directed ADAPT conditions. The study randomly allocates 360 NGR families across the three conditions ($n = 120$ per group). For the 6-month assessment, we estimate a projected 5% attrition rate and over the 24-month follow up we expect roughly 15% attrition. In two prior PMTO randomized trials with intensive multiple-method family assessments, family retention was 88% and 86%, respectively, at 30-month follow-ups [2, 12]. In both of those studies, there were no differential rates of attrition between intervention and controls, there was less than 5% attrition by the immediate 6 month post-test assessment, and less than 15% attrition by the 24 month assessment. Using an alpha level of .05 and considering 5% attrition over the first 6 months, a pre-post design with 3 groups of 114, within subject $SD = 1$, and between groups $SD = .71$; the study is powered .81 to minimally detect a small group by time interaction effect ($ES = .12$), small time effect ($ES = .15$), and small group effect ($ES = .21$) for given parenting, child, couple or parent constructs.

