assessments with the target 5-12 year old child, and complete parent-child observational tasks, and adult measures (approximately 100 minutes total). Families who prefer assessment outside the home may go to the local UMN or UM project office.

Note: Child care is offered to families for the siblings that are not participating in the research. In the event that child care staff are not available we will offer families a \$30 gift card stipend to provide their own child care during the in-home assessment.

5. Teachers will be contacted (at each time point) via secure, encrypted email, with an explanation of the study, and a copy of the parent's release of information. They will be directed to the study website to complete questionnaires. Teachers not responding will receive materials by mail, with follow-up calls. Teachers who do not want their compensation may choose to give the gift card back to ADAPT or to MCEC.

6. Following BL assessment, participants are electronically given random assignment to the G, W, or F study conditions, with 120 families assigned to each condition. The group condition will be run in three cohorts, with 2 groups of up to 10 families in each cohort of 20 families (up to 60 families in each of the two sites – i.e. 120 total, considerably more than we estimate will participate). In both online conditions, families may participate as they enter the study. However, given the necessity of running groups in cohorts and the need for equivalence in analysis, we will also assign individuals in the web conditions to a cohort.

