12.0 Recruitment Methods

12.1 Recruitment Process:

Recruitment flyers promoting the study will be distributed to our partners (NG, VA, M-SPAN). In addition, the PI has been invited by the MN ARNG to present at reintegration workshops which are mandatory for all soldiers returning from OEF/OIF deployment, and flyers will be handed out there. Flyers provide the phone and email contact information for the researchers, and the study site URL. The website guides parents to a brief explanation of the project, and a description of project confidentiality and its limits. Refer a friend post cards will be distributed to previous ADAPT study participants and current participants (as recruitment occurs). A recruitment/outreach booth will be set-up at the MN State Fair on Military Appreciation Day.

Interested participants will be directed to an anonymous online screening instrument. This screen determines eligibility based on the above stated inclusion and exclusion criteria. Eligible participants will next complete a brief contact information form, followed by an online informed consent that will provide information about study risks, benefits and about the possibility of being randomly assigned to either an intervention (E) group or SAU comparison group. In reintegrating families with two at-home participating parents/caregivers, each will complete a separate informed consent.

PROTOCOL TITLE: Comparing Web, Group, and Telehealth Formats of a Military Parenting Program

VERSION DATE: May 4, 2018

Eligible participants will next complete a brief contact information form, followed by an online informed consent providing information about study risks, benefits and the possibility of being randomly assigned to one of three intervention conditions: group-based ADAPT (G), web-only/self-directed ADAPT (W), or individualized web-facilitated ADAPT (F). In reintegrating families with two at-home participating parents/caregivers, each will complete a separate informed consent.

Consenting participants will be provided a contact number to speak to the PI or study coordinator with questions. Families requesting a telephone screening will be asked for verbal consent for the team to maintain contact through reminder emails and phone calls as needed to complete informed consent and BL online assessments. Informed consent may also be completed at the in-home assessment.

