- Interested participants will be directed to an anonymous online screening instrument. This screen determines eligibility based on the inclusion criteria mentioned above. To be eligible for the study, families must agree to random assignment to experimental or control conditions, be willing and able to complete assessment and intervention, and live within the catchment area. See Inclusion/Exclusion Criteria for eligibility guidelines.

- Eligible adult family participants will next complete a brief contact information form, followed by an online informed consent that will provide information about study risks, benefits and about the possibility of being randomly assigned to one of the three conditions. Families will be assured that no services or relationship

PROTOCOL TITLE: Comparing Web, Group, and Telehealth Formats of a Military Parenting Program

VERSION DATE: May 4, 2018

with the NG or the University of Minnesota or University of Michigan will change or be adversely affected regardless of whether or not they choose to participate in the study.

- The voluntary nature of participation and the ability to withdraw from the project at any time without penalty will be emphasized. In reintegrating families with two at-home participating parents/caregivers, each will complete a separate informed consent.
- Consenting adult family participants will be provided a contact number in order to speak to the PI or study coordinator with any questions. Families who request a telephone screening (e.g., families whose internet is not accessible at the time of the call) will be asked for verbal consent for the research team to maintain contact through weekly reminder emails and phone calls as needed to complete informed consent and baseline (BL) online assessments. Where informed consent is not completed prior to the home visit, it may be completed at the beginning of the in-home assessment.

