The anticipated potential adversity inherent in assessment is limited to those situations described above and is addressed by the timely intervention of a licensed clinical psychologist skilled in risk assessment and mandatory reporting requirements.

We have never had a staff safety issue while in a subject's home and have done more than 500 in-home assessments to date. In our assessment tech training, our techs are given a manual with instructions for dealing with different situations, and we do discuss this issue so all of our techs know what to do in case of an emergency.

As a part of the ongoing statistical analyses conducted to evaluate the effectiveness of the prevention trial, the experimental and control groups will be routinely compared on several dimensions, including the occurrence of the type of adverse events described above. With any significant group difference, the relevant covariates will be thoroughly examined in order to understand more completely the relationship between the variables of interest and potential effects of the intervention. The results of our analyses, including the occurrence of adverse events, will be reported both to our IRB and to NIDA through annual progress reports. We will also report adverse events to others, as directed by our IRB or NIDA Program Official.

Reporting Procedure for Serious Unanticipated Adverse Events

In the event of an unanticipated serious adverse event, the project PI will ensure that these events are reported to the NIDA Program Official within 24 hours by phone, fax, and/or email and will submit a written report to the Program Official no more than two days later. The project staff will also utilize the following reporting procedures:

1. When the grant staff and/or PI become aware of a serious adverse event, reporting requirements must be implemented in a timely manner.

PROTOCOL TITLE: Comparing Web, Group, and Telehealth Formats of a Military

Parenting Program

VERSION DATE: May 4, 2018

2. PI completes a University of Minnesota "Adverse Event Reporting Form" and submits the form to the Human Subjects Officer at the U of Minnesota.
3. The Human Subjects officer immediately distributes the form to the following individuals or groups as required: Center Administrator, Center Management Committee, and Center IRB Officials.

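### Consent and safety text refers to an SAU or control group that this trial of three active ADAPT arms does not have; the passages must be reconciled and the arms in the adverse-event comparison named.

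*Protocol*

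**What the plan says.** The design sections of the protocol are consistent with one another. Section 1.1 states: "The study will randomly allocate 360 NGR families to one of three conditions". The conditions are group-based, individualised web-facilitated and self-directed web ADAPT. The Aim 1 analysis text repeats this ("The study randomly allocates 360 NGR families across the three conditions"), and 5.2 (item 6) has the electronic assignment made "with 120 families assigned to each condition".

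Other sections describe a two-group trial:

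- **12.1 and 23.3, consent content.** The online consent will tell families they may be "randomly assigned to either an intervention (E) group or SAU comparison group". In 12.1 the next paragraph gives a different account of the same consent, in which families are "randomly assigned to one of three intervention conditions: group-based ADAPT (G), web-only/self-directed ADAPT (W), or individualized web-facilitated ADAPT (F"). In 23.3 no correct version follows.
- **14.1, agreement to randomisation.** "families must agree to random assignment to experimental or control conditions". The next bullet speaks of three conditions.
- **14.1, adverse events.** "the experimental and control groups will be routinely compared on several dimensions". Adverse events are one of those dimensions, and results go to the IRB and NIDA in annual progress reports.
- **22.1, programme consent.** "Subjects who are randomized to the experimental (intervention) condition will complete an additional consent". A route is then given for the in-person groups and for web-facilitated families, but none for Self-Directed families.

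**The concern.** Three parts of the protocol that people act on name groups the trial does not contain.

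The first is what families are told. The protocol should give one account of the consent content; it gives two that cannot both be true. If the live screen was built from 12.1 (first account) or 23.3, families were told of a comparison arm that does not exist.

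The second is the safety comparison. Section 19.0 marks provisions for monitoring data for participant safety as not applicable, so the sentence in 14.1 is the only between-group comparison of adverse events that the protocol states. Whoever runs it has to decide which arm or arms count as control, and the protocol does not say.

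The third is the programme consent. Section 22.1 and item 8 of 5.2 do not agree for the Self-Directed arm, which is 120 of the 360 families, or one third of the sample.

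**Working it through.** The only arithmetic is the allocation count. The rest is a comparison of sections.

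**1. Is there room for another arm?** Inputs: 360 families in total (1.1 and the Aim 1 analysis text) and 120 per condition in three conditions (5.2, item 6).

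- Families in ADAPT arms: 3 × 120 = 360, which reproduces the protocol's own total.
- Families left for an SAU or control arm: 360 − 360 = 0.

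The abbreviation SAU is not expanded anywhere in the protocol, and no untreated or usual-services arm is described.

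**2. Could control mean Self-Directed?** The growth model in section 1.0 uses Self-Directed as the omitted reference group. It is still an ADAPT format, with the full ten-module website. The protocol never calls it a control, and nothing links the word control in 14.1 to it.

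**3. Consent content, section by section.**

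- 5.2, item 1: three ADAPT conditions.
- 12.1, second account: three ADAPT conditions.
- 14.1, bullet on eligible adults: three conditions.
- 12.1, first account: intervention or SAU.
- 23.3: intervention or SAU.

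Three statements match the design and two contradict it. Section 12.1 contains one of each.

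**4. Eligibility.** The formal inclusion criteria in 9.1 ask only that families agree to randomisation. The experimental-or-control wording is in the narrative of 14.1, which refers the reader back to the eligibility criteria. The conflict therefore lies within 14.1 and does not reach the formal criteria.

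**5. Adverse-event comparison.** Section 14.1 names two groups and the design has three. Neither group is defined, so the sentence does not determine which contrast is to be made.

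**6. Programme consent.** Under 5.2, item 8, Self-Directed families complete an informed consent form on the ADAPT website before they reach the dashboard. Under 22.1, the additional consent belongs to the experimental condition and is collected at the first group session or online for web-facilitated families. Read literally, 22.1 leaves out an arm that 5.2 includes.

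**The case against.** The strongest reply is that this is leftover terminology with no demonstrated effect. Section 5.2, which governs procedures, is correct. In 12.1 and 14.1 the correct wording directly follows the wrong wording. Section 23.3 largely repeats the recruitment text of 12.1. Section 22.1 covers videotaping as well as programme participation, and Self-Directed has no live facilitator sessions to record, so its omission there may be only a missing cross-reference. The arms for the safety comparison might also be named in a statistical analysis plan that was not available for this review.

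Much of this stands. The consent pages were not available, so it cannot be said that any family was in fact misinformed. The gap in 22.1 does not show that the sponsor regards Self-Directed as a control. What does not stand is that the text can be left alone. Consent content and the groups in a stated safety comparison are operative protocol text, and the two-group wording appears in five places across four sections. An analysis plan could add detail, but the protocol sentence would still name groups that do not exist.

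A reader might infer three stronger things, none of which the documents support:

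- **Expectancy bias in favour of Hypothesis 1**, with Self-Directed families seeing themselves as the lesser arm. This needs the live consent to carry the SAU wording and families to equate SAU with Self-Directed; neither is shown. Those families receive a programme introduction, a programme consent and ten modules, and could equally see themselves on the intervention side, so even the direction is open. Observation and teacher report are also collected at T1, T3 and T4.
- **That the adverse-event comparison cannot be done.** It is undefined, not impossible. Once the arms are named it can be run.
- **That Group and Facilitated will be pooled, hiding an excess in one of them.** Section 14.1 does not say so, and the documents give no event rates from which such masking could be sized.

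**Conclusion.** The contradiction is established from the protocol's own text. Three arms of 120 use up all 360 families, yet 12.1 and 23.3 describe an SAU group and 14.1 refers to control conditions and a control group.

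Two consequences follow, both limited. Families may be misinformed, on the condition that the live consent follows the SAU wording; this review could not check it. And the only between-group safety comparison the protocol states has undefined groups. Separately, 22.1 and 5.2 need reconciling on the Self-Directed programme consent.

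No bias or error rate can be attached to any of this from the documents. Sample size, power and alpha do not change. The correction should be made because it concerns what families are told and which arms are compared for harm.

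**What to change.** - **12.1 and 23.3:** delete the sentence describing an intervention group and an SAU group. Use the three-condition sentence from 5.2, item 1, in both places.
- **Live consent screen:** check that it describes the three ADAPT formats and no SAU or comparison group.
- **14.1, agreement to randomisation:** replace the experimental-or-control wording with the three ADAPT formats.
- **14.1, adverse events:** state that adverse events are compared across Group, Facilitated and Self-Directed as three separate arms.
- **22.1:** reconcile with 5.2, item 8, so that both sections say the same about how and where Self-Directed families give programme consent, and whether the videotaping element applies to them.

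The cost is protocol wording, plus a consent amendment if the live screen proves wrong. No new data are needed.
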